## **MATERIAL AND METHOD**

This study will be completed after receiving permission from "Dokuz Eylül University Faculty of Medicine Clinical Research Ethics Committee" and "Medical Device Study and Authorization Coordination Department", (Protocol No: 266-SBKAEK) with informed patient consent, as a prospective, randomized and double-blind study of 102 patients in ASA classification group I-II, aged from 18 to 65 years undergoing elective laparoscopic gynecological surgery.

Patients will be divided as

Group 1 => i-gel (51 patients) (control group)

Group 2 => LMA-Supreme (51 patients) (experiment group).

Patients and surgeons performing the operations will not be aware of the airway device used. Patients in the groups will be determined with the block randomization method. By looking at a simple random number table, 102 individuals will be divided into 2 groups of 51 by using 6 blocks of groups containing.

Before anesthesia induction patients taken to the operating room will have standard monitoring applied (non-invasive blood pressure measurements, electrocardiogram, peripheral oxygen saturation measurements). For preoperative sedation 0.02 mg/kg midazolam IV will be administered. Patients will be preoxygenized for 3 minutes with 6 L/min oxygen through a face mask. For anesthesia induction after 2 minutes of 0.2  $\mu$ kg/min remifentanil and 6 mg kg propofol infusion, IV 1-2 mg kg propofol will be administered. After induction patients will be ventilated with a face mask with 6 L/min 100% oxygen.

All patients will have bispectral index monitoring (BIS, ASPECT A-2000 BIS XP monitor) to standardize anesthesia depth. BIS values will be held between 40-60. BIS values will be kept within this interval by increasing or decreasing propofol infusion by 1 mg/kg after additional bolus dose of propofol (1 mg/kg).

Airway device insertion will be performed by two researchers with more than 5 years experience.

During airway device insertion, if necessary depending on patient reaction additional doses of 0.5 mg/kg propofol will be administered.

Anesthesia maintenance will be ensured by 50% O2/air with 0.1-0.4  $\mu$  kg/min remifentanil and 50-150  $\mu$  kg/ min (4-10 mg/kg/hr) propofol IV infusion (29).

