Positive pressure respiration using a ring system will begin with 2-4 L/min fresh gas flow and FiO2 0.5 volume control with 6-8 ml/kg tidal volume and 10 respirations/min frequency.

PEEP will not be applied and I:E ratio will be 1:1,5. ETCO2 will be held from 35-45 mmHg, if necessary first respiration frequency will be increased, later tidal volume will be increased. For laparoscopic intervention, permission will be given for CO2 insufflation for peritoneal interior pressure of 15 mmHg.

Two minutes after insertion of LMA-Supreme or i-gel, before insufflation, 10 minutes after insufflation and trendelenburg position, immediately before peritoneal desufflation and before removing the airway device, ventilation parameters will be assessed.

**Respiratory Measurements recorded:** Tidal volume (TV), respiration rate (RR), peripheral oxygen saturation (SPO2), end-tidal carbon dioxide pressure (PETCO2), peak airway pressure (Ppeak), mean airway pressure (Pmean) and expiratory volume per minute (VE).

**Hemodynamic Measurements recorded:** (Simultaneous to the above measurements and additionally before induction) systolic arterial pressure (SAP), diastolic arterial pressure (DAP), mean arterial pressure (MAP), and heart rate (HR).

**Evaluation related to stomach probe:** Immediately after the airway device is inserted, through the LMA-Supreme (14F for size 3 and 16F for sizes 4 and 5) and i-gel drainage tube a 12F orogastric tube will be advanced to the stomach and stomach contents aspirated. The ease of insertion of stomach probe and amount of aspirated fluid will be recorded. Ease of insertion of orogastric tube will be classified as very easy, easy, difficult or very difficult by the administrator (9). Gastric aspiration will be 200 cmH2O during 10 seconds by a suction; (connecting it later to a collection bag).

The number of interventions of verres needle, initial intra-abdominal pressure, time for intra-abdominal pressure to reach 15 mmHg, and volume of insufflated CO2 will be recorded. Sufficiency of pneumoperitoneum during operation (sufficient/insufficient), and quality of surgical view will be assessed with points from 1 to 4 by the surgeon blind to the airway device (24).

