Stomach distension will be assessed on a scale of 0 to 10 (0= empty stomach, 10= distension obstructing view of the surgical field) by a surgeon blind to the airway device immediately after insertion of the laparoscope into the abdomen and immediately before the end of peritoneal insufflation and the difference between the scores at the start and end of surgery will be recorded (15). Operation table positioning (Trendelenburg) will be limited to a maximum 30°.

When the patient is cooperative, the LMA-Supreme or i-gel will be removed and total anesthesia duration and peritoneal insufflation duration will be recorded. Complications that may develop during airway device removal (cough, vomiting, laryngeal stridor, laryngeal spasm or airway intervention requirements) will be recorded.

After removing the SGAD, the presence of blood will be assessed as:

- 1: no blood
- 2: trace amounts of blood
- 3: clear amounts of blood

Conscious patients will be taken to the recovery unit and a blind researcher will evaluate throat pain, voice loss and difficulty swallowing in the 1st and 24th hours. For evaluation of throat pain, VAS-10 (visual analog scale) will be used.

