## Statistical Analysis

In a study that was conducted by Seet et al., power was calculated as 90% as a result of the power analysis that was made for laryngeal mask airway  $OLP = >21 +/- 5 \text{ cmH}_2\text{O}$  average values; and the number of the case was determined to be 40 for each group (30).

The data have been evaluated with the SPSS (Statistical Package for Social Sciences) 15.0 package program. The fitness of the variables to normal distribution was tested with the Kolmogorov Smirnov Test. The t-test was used to compare the two groups that fit normal distribution; and the Mann Whitney U-Test was used for those that did not fit normal distribution. The variables that were defined with numbers were evaluated with the Chi-Square Test and with the Fisher's Exact Test when needed; and the significance level was taken as  $p < 0.05$ . The mean, standard deviation, median, min. and max. values of the continuous variables and their sub-groups were presented; and the frequency numbers and percentages of the class variables were presented.

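### Haemodynamic comparisons leave a pre-device baseline unused, and the stomach distension difference measures only the change after laparoscope entry

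*Combined protocol and SAP*

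**What the plan says.** **Haemodynamics.** In MATERIAL AND METHOD (Combined protocol and SAP), SAP, DAP, MAP and HR are recorded at the ventilation time points and once more ahead of them: "Simultaneous to the above measurements and additionally before induction".

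**Stomach distension.** The same section states: "Stomach distension will be assessed on a scale of 0 to 10". The rating is made blind to the device, at two moments: "immediately after insertion of the laparoscope into the abdomen and immediately before the end of peritoneal insufflation". Of these two scores, "the difference between the scores at the start and end of surgery will be recorded".

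**Analysis.** The Statistical Analysis section names no variable and gives one rule for continuous data: "The t-test was used to compare the two groups that fit normal distribution", with the Mann-Whitney U test otherwise. It names no model containing a covariate and no separate analysis of the distension score at the end.

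**The concern.** There are two points about how a preceding value enters a comparison.

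First, the pre-induction haemodynamic values cannot have been affected by the device, so they are proper baseline covariates. With only unadjusted tests named, nothing in the plan uses them to sharpen the comparison of later values.

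Second, the distension start score looks like a baseline but is not a pre-device one. By the time the surgeon first sees the stomach, the device has been in place, the stomach has been emptied through it and the patient has been ventilated through it. If one device lets more gas into the stomach during that period, or drains it less well, the difference is already in the start score. Subtracting that score removes it. If only the difference is kept and analysed, a reader could conclude that the devices are alike on stomach inflation when they are alike only from laparoscope entry onward.

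**Working it through.** **Inputs.** There are 51 patients per arm, 102 in total (MATERIAL AND METHOD). The documents give no SD, correlation or expected difference for haemodynamics or distension, so there is no figure of the plan's own to reproduce here. The stated 40 per group at 90% power is for leak pressure and does not enter. All correlations, SD ratios and effect sizes below are assumptions.

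**Step 1: haemodynamics.** Let r be the within-arm correlation between the pre-induction value and a later value. Take the variance of the unadjusted arm difference as 1. With the baseline in a linear model the large-sample variance is 1 − r².
- r = 0.3: 1 − 0.09 = 0.91, a 9% reduction. The 51 per arm then work like 51 / 0.91 = 56.
- r = 0.5: 1 − 0.25 = 0.75, a 25% reduction. The 51 per arm then work like 51 / 0.75 = 68.

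Chance imbalance in the covariate costs a factor of about 1 + 1/(102 − 4) = 1.01, so adjustment gains whenever r exceeds about 0.1.

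**Step 2: what precedes the distension start score.** In the protocol's order:
1. Mask ventilation: "After induction patients will be ventilated with a face mask".
2. Device insertion.
3. Gastric suction through the device's channel: "orogastric tube will be advanced to the stomach and stomach contents aspirated".
4. Ventilation through the device, with parameters assessed before insufflation.
5. The first score, given "by a surgeon blind to the airway device immediately after insertion of the laparoscope into the abdomen".

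The start score is therefore a post-randomisation, post-device value.

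**Step 3: what each summary estimates.** Let e be a device effect present at the start score and persisting to the end, and l the effect added afterwards.
- End score: e + l.
- Difference: (e + l) − e = l.
- End score adjusted for start score, with slope b: e + l − b·e.

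With e = 1 and l = 1 these are 2, 1 and (at b = 0.5) 1.5. With e = 1 and l = 0 the difference shows nothing, while the end score shows 1.

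**Step 4: would adjusting for the start score serve instead?** Let k be the start SD divided by the end SD, and set the end-score variance to 1. The variance is 1 + k² − 2rk for the difference and 1 − r² for the adjusted estimate. If the device has shifted the start score by d start-SDs, the adjusted variance is multiplied by about 1 + d²/4. The slope is b = r/k.

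| k | r | Difference | Adjusted, d = 0 | Adjusted, d = 1 (×1.25) | Slope b |
|---|---|---|---|---|---|
| 1 | 0.3 | 1.40 | 0.91 | 1.14 | 0.3 |
| 1 | 0.5 | 1.00 | 0.75 | 0.94 | 0.5 |
| 1 | 0.7 | 0.60 | 0.51 | 0.64 | 0.7 |
| 0.5 | 0.5 | 0.75 | 0.75 | 0.94 | 1.0 |
| 0.5 | 0.7 | 0.55 | 0.51 | 0.64 | 1.4 |

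With no shift the adjusted estimate is at least as precise as the difference. With a shift of one SD it is less precise in three of the five rows. With b = 1.4 it removes more than the whole of e: e = 0.5 and l = 0.5 give 1.0 − 1.4 × 0.5 = 0.3, against 0.5 for the difference.

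**Step 5: what the unadjusted end score costs.** Its variance is 1. The difference has the smaller variance when 1 + k² − 2rk < 1, that is, when r > k/2: above 0.5 for equal SDs and above 0.25 when the start SD is half the end SD. The end score is recommended for the effect it estimates, not because it is always more precise.

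**The case against.** The difference answers a legitimate question: how much distension accrues during pneumoperitoneum. The protocol cites a source for the measure. No pre-device score on this scale is possible, because the surgeon sees the stomach only through the laparoscope. Mask ventilation and suction also feed into the start score, so not all of it is due to the device. All of this stands. It supports keeping the difference under an accurate label. It does not make the difference a measure of the total device effect.

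The text also says only that the difference is recorded, and the Statistical Analysis section lists no variables. That the difference alone will be compared, or that the pre-induction values will go unused, is an inference. Both distension scores are assessed, so nothing need be lost.

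A reader might go further and infer that the end score should be adjusted for the start score, on the ground that this is never less precise than the difference and always removes less of an early effect. The documents do not support that. The precision claim assumes that the device has not moved the start score, which is the very possibility at issue, and the claim about removal needs a slope below 1; Step 4 shows both failing under plausible assumptions. A precision gain of 25% to 35% over the difference (r = 0.5 to 0.3) arises only with equal SDs and no early effect. If suction leaves most start scores near 0, equal SDs are doubtful.

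**Conclusion.** The point holds in two limited parts.

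For haemodynamics, adjustment for the pre-induction value gains precision from data already collected: about 9% to 25% less variance for an assumed r of 0.3 to 0.5. The unadjusted comparison is not biased, since allocation is randomised; it is only less efficient.

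For distension, the cancellation of an early persisting effect is exact algebra and follows from the protocol's own sequence. Whether such an effect exists, and how large it would be, the documents do not say. This is not evidence that the planned difference is invalid, only that it has a narrower meaning than its place among the device comparisons suggests.

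The importance is low. The power statement concerns leak pressure, so neither part affects the outcome on which the trial was sized.

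**What to change.** Add to the Statistical Analysis section:
- **Haemodynamics:** compare each later SAP, DAP, MAP and HR value between arms with a linear model containing arm and the pre-induction value of the same variable.
- **Distension, total device effect:** compare the end score between arms without conditioning on the start score. The t-test or Mann-Whitney test already named will do.
- **Distension, start score:** report it by arm as an outcome in its own right.
- **Distension, difference:** keep it, labelled as intraoperative change.

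In MATERIAL AND METHOD, state that both raw distension scores are recorded as well as their difference. If only the difference were stored, an early device effect could not be recovered.

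The cost is a few lines of text and a little more analysis. No new measurement is needed.

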**Criteria:**

**Inclusion Criteria:**

- 1. American Society of Anesthesiologists classification group I-II
- 2. between 18-65 years
- 3. undergoing elective laparoscopic gynecological surgery

**Exclusion Criteria:**

- 1. Those with any neck or upper respiratory tract pathology
- 2. Those at risk of gastric content regurgitation/aspiration (previous upper Gastrointestinal system surgery, known hiatus hernia, gastroesophageal reflux, history of peptic ulcers, full stomach, pregnancy)
- 3. Those with low pulmonary compliance or high airway resistance (chronic pulmonary diseases)
- 4. Obese patients (BMI >35)
- 5. Those with throat pain, dysphagia and dysphonia
- 6. Those with possible or previous difficult airway
- 7. Those with operations planned for longer than 4 hours

8. Conversion to laparotomy

9. Neuromuscular blocking agent used

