Many anesthetists choose not to use neuromuscular blocker agents unless necessary for surgical procedures in routine application. As the clinical view is generally based on personal experience, the use of both neuromuscular agents and the dose management of these agents may vary between clinicians. As a result making any specific recommendation is difficult. Chassard et al. evaluated 50 patients undergoing laparoscopic gynecological surgery with TIVA anesthesia management. In this study patients were divided into 2 groups as those given neuromuscular blocker agent (atracurium) and those not given it. In terms of operation conditions, an evaluation by surgeons found no difference between the two groups (32). The use of neuromuscular blockers in gynecological laparoscopy was found not to affect the majority of hemodynamic and respiratory changes due to pneumoperitoneum or operation conditions (33, 34).

Chen et al. (35) in a broad-series laparoscopic gynecological study (n=120) used ProSeal™ as SGAD and administered neuromuscular blocker agents to half of patients (rocuronium). The results of this study showed that both ventilation and surgical conditions were the same in both groups. The authors additionally noted that the use of neuromuscular blockers in laparoscopic gynecological surgeries was not beneficial as they did not reduce the operation and recovery times. In this study they emphasized the important point of easy insertion of laryngeal mask without neuromuscular blockers. Another study questioning the use of neuromuscular blockers in laparoscopic gynecological surgeries was completed by Swann et al. This study administered inhalation anesthesia for maintenance. The patients were divided into 2 groups. While spontaneous respiration and ventilation were ensured together without using neuromuscular blocker agents in the group with laryngeal mask inserted, controlled ventilation was

applied to the group with endotracheal intubation administered atracurium. There was no significant difference found between the groups in terms of intraoperative conditions; however a limitation of this study is the very short mean surgical duration (average < 15 min).

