## **AIM**

To compare the effects of i-gel and LMA-Supreme on ventilation parameters and surgical view during laparoscopic gynecological surgery in cases administered positive pressure ventilation without the use of neuromuscular agents.

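### Exclusion items 8 and 9 can remove allocated patients, with their recorded data, on intraoperative events that may depend on the device, and no analysis set is defined

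*Combined protocol and SAP*

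**What the plan says.** The Exclusion Criteria section lists nine items. Items 1 to 7 can be judged before surgery; item 7, for example, is worded prospectively: "Those with operations planned for longer than 4 hours". Item 8 is "Conversion to laparotomy" and item 9 is "Neuromuscular blocking agent used". Neither carries a time point or a reason.

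Under Material and Method, "102 individuals will be divided into 2 groups of 51" by block randomisation. The drug schedule there contains no neuromuscular blocker. The Aim is to compare the devices "in cases administered positive pressure ventilation without the use of neuromuscular agents".

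The same section schedules the oropharyngeal leak pressure (OLP) test before insufflation, 10 minutes later and just before desufflation. Throat symptoms are scored at 1 and 24 hours by a blinded researcher. After three failed insertion attempts the patient is intubated, and ease of insertion has a category for unsuccessful cases.

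The Statistical Analysis section gives a sample-size sentence, the tests and the descriptive statistics. It names no analysis set and has no rule for missing data or for patients who meet item 8 or 9. No other section supplies one.

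**The concern.** An eligibility criterion is applied before allocation and cannot depend on the device. An event after allocation can. The trial is meant to measure ventilation and surgical view without a blocker, and poor ventilation or poor view is an obvious reason to give one. The protocol's background makes the link itself: "Many anesthetists choose not to use neuromuscular blocker agents unless necessary for surgical procedures in routine application". Excluding patients because a blocker was given may therefore remove some of the failures that the trial is designed to count.

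If removal differs by arm and is linked to poor results, the comparison is between selected groups. The usual direction is toward no difference, because the worse device loses more of its poor results, but a difference can also be created where none exists. Without a named analysis set, two analysts could also defensibly analyse different patients.

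**Working it through.** **1. Timing of items 8 and 9.**
- Item 8: conversion requires that laparoscopy has begun. The device is allocated before insertion and inserted before laparoscopy. The time of randomisation is not stated, but on any reading item 8 applies after allocation.
- Item 9: the past participle, the position after item 8 and the absence of a blocker from the drug schedule all favour an intraoperative reading. A blocker planned before allocation cannot be ruled out.

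**2. Plausibility of device dependence.**
- Item 9: inadequate ventilation or view could prompt a blocker, and the anaesthetist securing the airway is not stated to be blinded. Failed insertion is a second possible route. The background section contrasts supraglottic devices with the tracheal tube technique on the need for a blocker, but also says the airway can be secured by tube without one. Whether item 9 applies to intubated patients is not stated.
- Item 8: "Patients and surgeons performing the operations will not be aware of the airway device used", and the device is covered after placement. This limits decisions influenced by knowing the device. It does not remove a true effect of the device on operating conditions.

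**3. What would be lost.** The pre-insufflation OLP and the insertion outcomes will usually have been recorded before either event, and the throat scores can still be collected afterwards. Excluding the patient discards all of them.

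**4. The plan's own figure.** The Statistical Analysis section attaches 90% power to 40 per group with SD 5 cmH2O, without stating a difference, so 40 cannot be reproduced. Solving for the difference (normal approximation, two-sided 0.05 assumed):

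difference = 5 × (1.960 + 1.282) × √(2/40) = 3.62 cmH2O

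The exact t-test gives about 3.67, with power about 0.96 at 51 per arm. Each arm could lose 51 − 40 = 11 patients (11/51 = 21.6%) before falling below 40, although the documents do not call this an allowance. Loss of numbers is therefore not the main problem; selection is.

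**5. How the bias depends on the unknowns (all rates assumed).** Suppose a fraction q of an arm is removed on a latent score that has correlation ρ with OLP, low values being removed. The arm's mean then rises by

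shift = 5 × ρ × φ(z_q) / (1 − q)

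For q = 0.10, φ(z_q) = 0.1755 and the shift is 0.975ρ. For q = 0.05, φ(z_q) = 0.1031 and it is 0.543ρ. The bias is the difference in shifts. With no true difference, 51 per arm and a two-sided z-test at 0.05:

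| Removed, arm A v arm B | ρ | Bias (cmH2O) | False-positive rate |
|---|---|---|---|
| 10% v 10% | any (equal in both arms) | 0 | 0.050 |
| 5% v 10% | 0.3 | 0.13 | 0.052 |
| 5% v 10% | 1 | 0.43 | 0.070 |
| 0% v 10% | 0.3 | 0.29 | 0.060 |
| 0% v 10% | 1 | 0.97 | 0.160 |

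ρ = 1 is the extreme in which exactly the worst seals are removed. The table shows only that the bias needs removal to be both unequal and strongly linked to the outcome. It does not estimate what will happen in this trial, and it is not evidence of gain from the fix for later OLP readings.

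**The case against.** **The bias may be trivial.** No event rates are given. Surgeons are blinded and the device is covered. Of a cited comparison with and without a blocker, the background says: "In terms of operation conditions, an evaluation by surgeons found no difference between the two groups". All of this stands, and it rules out any claim about size.

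**Certainty and device dependence fall on different items.** Item 8 is clearly after allocation but has the weaker device link; item 9 has the stronger link but unclear timing. This is fair. It is a reason to clarify item 9, not to leave both as they are.

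**The Aim concerns performance without a blocker, so dropping readings taken under one is consistent with it.** That is correct for those readings. It does not justify dropping what was measured beforehand, or hiding how often each device led to a blocker.

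**The remedy does not cure everything.** Later OLP and ventilation readings from affected patients are either missing or not no-blocker results. Under the planned t-test or Mann-Whitney test such patients drop out of those comparisons, so that selection remains. This stands.

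**Counting a blocker as an unfavourable result carries its own risk.** It relies on a reason recorded by someone not stated to be blinded. Take an assumed unfavourable rate of 15% in both arms, and suppose 10% of the favourable cases in one arm only get an unneeded blocker. That arm becomes 15% + 0.10 × 85% = 23.5%, and the false-positive rate of Fisher's test rises from 0.024 to 0.134. That rule therefore belongs in a sensitivity analysis at most.

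**Conclusion.** The point holds as a defect of specification. Item 8 allows an allocated patient to be removed on any reading, item 9 does so on its most natural reading, and no analysis set says otherwise. The amount of bias is unknown. It is negligible if removal is rare or equal by arm, and material only if removal is unequal and strongly tied to the outcome.

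A reader might infer more than the documents support:
- That the comparison will be biased, or that power will fall materially. There are no event rates, and on the plan's own 90% at 40 per group, 51 per arm leaves room for losses.
- That the surgical-view comparison would lose a calculable amount of power. The protocol scores view from 1 to 4 and rates only pneumoperitoneum as sufficient or insufficient, so a calculation on insufficient view uses a dichotomy the plan does not contain.
- That intubation after failed insertion contradicts item 9. The protocol mentions no relaxant for it; how item 9 applies is simply not stated.

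The conclusion rests on reading item 9 as intraoperative and on device dependence being plausible, not shown.

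**What to change.** 1. Move items 8 and 9 out of the Exclusion Criteria and list them as events after allocation. Keep item 9 as an eligibility criterion only if it means use planned before allocation, and say so.
2. State in the Statistical Analysis section that all randomised patients are analysed in their allocated group.
3. Keep every measurement taken before the event, including insertion outcomes and the pre-insufflation OLP, and keep the 1- and 24-hour throat scores. Count failed insertion as unsuccessful whether or not a blocker was then given.
4. Do not present readings or scores obtained under a blocker or after conversion as no-blocker results. Flag them, and state that comparisons of later OLP and ventilation readings remain open to selection because valid readings are missing for affected patients.
5. Report blocker use and conversion, each with its reason, and intubation, by arm as outcomes.
6. Give the analysis without these patients as a sensitivity analysis only. One counting a blocker given for inadequate view or ventilation as unfavourable may be added on the same footing.

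The cost is two lines moved, a short analysis-set paragraph and one recorded reason per event, with no extra patients or procedures. The downsides are a little noise from purely surgical conversions and some missing later readings.
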